8.3. Classification of an Adverse Event

8.3.1. Severity of Event

Assessment of severity of an AE will be rated according to the definitions below in Table 8 and the worst grade documented.

Table 6: Definitions of AE Severity

Mild:	Events require minimal or no treatment and do not interfere with the participant's daily activities.
Moderate:	Events result in a low level of inconvenience or concern with the therapeutic measures. Moderate events may cause some interference with functioning.
Severe:	Events interrupt a participant's usual daily activity and may require systemic drug therapy or other treatment. Severe events are usually potentially life-threatening or incapacitating. Of note, the term "severe" does not necessarily equate to "serious".

8.3.2. Relationship to Ocular Surgical Procedure or Study Drug

Determination of the relationship (if any) between the AE and the study drug will be made using the guidelines presented in Table 7 and Table 8.

Table 7: Guidelines for Determining the Relationship (if any) between an Adverse Event and the Ocular Surgical Procedure

Related:	This causal relationship is assigned if the AE starts at a reasonable time during or after the surgical intervention and could reasonably be explained by the known characteristics of the surgical intervention.
Not Related:	This causal relationship is assigned when the time association or the subject's clinical state is such that the surgical intervention was not likely to have had an association with the observed AE.

Table 8: Guidelines for Determining the Relationship (if any) between an Adverse Event and the Study Drug

Definite:	This causal relationship is assigned if the AE starts a reasonable time after the administration of study drug, stops/improves when the study drug is stopped, and could reasonably be explained by known characteristics of the study drug.
Probable:	This causal relationship is assigned when the AE starts a reasonable time after the administration of study drug, stops/improves when the study drug is stopped, and could not be reasonably explained by known characteristics of the subject's clinical state.
Possible:	This causal relationship is assigned when the AE starts a reasonable time after the administration of study drug, but could be produced by the subject's clinical state or other modes of therapy administered to the subject.
Not Related:	This causal relationship is assigned when the time association or the patient's clinical state is such that the study drug was not likely to have had an association with the observed AE.

The attributability (relatedness) of an AE to the surgical procedure or to the study drug will be reported in the source documents and in the eCRF as described in Section 8.1.

8.3.3. Expectedness

An AE or a suspected adverse event (SAR) is considered "unexpected" if it is not listed in the APP13007 Investigator's Brochure or is not listed at the specificity or severity that has been observed. Expected events for APP13007 administration include those events described in Section 1.4.1 and the APP13007 Investigator's Brochure.

8.3.4. Action Taken with Study Drug

The action to be taken in response to an AE will be to either discontinue or continue study drug. Subjects will be permitted to restart study drug if there is a temporary interruption of study drug dosing not more than 1 day due to an AE. Decrease in the dose strength or dosing frequency of study drug is not allowed in this study.

8.3.5. Adverse Event Outcome

If an AE occurs, the Investigator will institute support and/or treatment as deemed appropriate.

The outcome of the adverse event will be categorized as follows:

- Resolved
- Resolved with sequelae
- Ongoing
- Death
- Unknown

The Investigator should make every attempt to follow SAEs to resolution.

8.4. Adverse Event Follow-up

If a non-serious AE is unresolved at the time of the subject's final study visit, the subject will still be discontinued from the study, but an effort will be made to follow up until the AE is resolved or stabilized, the subject is lost to follow-up, or there is some other resolution of the event. The Investigator should make every attempt to follow all SAEs to resolution.

8.5. Overdose/Under-dose

Overdose:

Dosing compliance will be assessed via a daily dosing diary completed by the subject and reviewed by the designated site personnel. If the subject reports over instillation of study drug, exceeding more than one drop (or equivalent) into the study eye per dose (further explained in Note below) or instillation of the study drug more than twice a day (when dosing BID) or more than once daily (when dosing QD) on two consecutive days or longer, this will be classified as an overdose event and a protocol deviation.

Note: As described in Section 5.1.2, if the subject misses the conjunctival cul-de-sac when dosing the first drop of study drug, the subject should use a tissue to wipe away the study drug around the eye and then instill a second drop into the conjunctival cul-de-sac. This will not be considered a protocol deviation or an overdose event. However, if the subject administers a third drop into the conjunctival sac, no matter if the second drop is missed, then this will be recorded as an overdose.

Under-dose:

Under-dosing will not be reported as a deviation until the subject has missed 2 consecutive doses (i.e. 2 consecutive missed doses in 1 day during BID dosing or 2 consecutive missed doses over 2 days during QD dosing).

8.6. Pregnancies

All female subjects enrolled into the study must be of non-childbearing potential. Therefore, no pregnancies should occur. If there is an unexpected pregnancy, it will be handled on a case-by-case basis by discussing with the Study Medical Monitor and then the Sponsor Medical Monitor.

Additionally, the Investigator should report the information to the Sponsor as per the procedures to be followed for an SAE. Although a pregnancy itself is not an SAE, it has potentially serious consequences in subjects exposed to investigational drugs that can result in an SAE.

The pregnancy and follow-up of the pregnancy must be reported on the appropriate pregnancy CRF and Pregnancy Reporting Form. The expected date of delivery or expected date of the end of the pregnancy, last menstruation, estimated fertility date, pregnancy result and neonatal data etc., should be included in this information.

The investigator will follow the medical status of the mother, as well as the fetus, as if the pregnancy is an SAE and will report the outcome to the Sponsor. Follow-up visits must continue until the end of the pregnancy, even if that lasts beyond the end of the study.

When the outcome of the pregnancy falls under the criteria for SAEs [spontaneous abortion, induced abortion, stillbirth, death of newborn, congenital anomaly (including anomaly in a miscarried fetus)], the investigator should respond in accordance with the report procedure for SAEs. Additional information regarding the outcomes of a pregnancy which are categorized as an SAE is mentioned below:

- "Spontaneous abortion" includes abortion and missed abortion.
- Death of an infant within 1 month after birth should be reported as an SAE regardless of its relationship with the study drug.
- If an infant dies more than 1 month after the birth, it should be reported if a relationship between the death and intrauterine exposure to the study drug is judged as "possible" by the investigator.

- In the case of a delivery of a living newborn, the "normality" of the infant is evaluated at birth.
- "Normality" of a miscarried fetus is evaluated by visual examination unless test results which indicate a congenital anomaly are obtained prior to miscarriage.

8.7. Serious Adverse Event Reporting

8.7.1. Reporting Requirements

It is the responsibility of the Investigators or their designees to report any event of this nature to the Sponsor or a designee within 24 hours of the event being brought to the Investigators' or their staffs' attention. It is also the responsibility of the Investigator to report all SAEs reported at their site to the IRB, as required. The Investigator should make every attempt to follow all SAEs to resolution.

All SAEs have to be reported, whether or not considered causally related to the investigational drug product, or to the study procedure(s). All SAEs will be recorded in the eCRF. SAEs will be recorded from the time of informed consent.

All Serious Adverse Events (SAE) must be reported, whether or not considered related to the study drug, on a separate SAE Report Form. All SAEs will also be recorded in the eCRF. The Sponsor will be responsible for reporting all SAEs to regulatory authorities and ethics committees (see NOTE below) in accordance with ICH Good Clinical Practice and local regulations. As soon as the Investigator is aware of a potential SAE he/she should contact [REDACTED] by fax or e-mail and in any case *no later than 24 hours* after the knowledge of such a case. At the time of initial reporting the Investigator must provide as a minimum requirement, subject number, birth date, description of the SAE and a preliminary assessment of causality.

For fatal or life-threatening adverse events where important or relevant information is missing, active follow-up is undertaken immediately. Investigators or other site personnel inform the Study Medical Monitor, the Sponsor, and the CRO for Study Management and Monitoring of any follow-up information on a previously reported SAE immediately but no later than within 24 hours of when the Investigator becomes aware of it. The Study Medical Monitor or Sponsor Medical Monitor will advise the Investigator/study site personnel how to proceed.

The SAE reporting procedures are detailed in the study specific Safety Management Plan. This plan is an agreement between the Sponsor, the CRO for Study Management and Monitoring and Drug Safety Navigator.

NOTE: If an unexpected SAE occurs at any one site that is determined to be related, probably related or possibly related to study drug, all study sites will be notified by the

Sponsor via the CRO for Study Management and Monitoring and each site will report it to the IRB.

8.7.2. Reporting of Suspected Unexpected Serious Adverse Reactions (SUSARs)

A suspected serious adverse reaction is any serious adverse event for which there is a reasonable possibility that the investigational product caused the adverse event. A serious adverse reaction is considered "unexpected" if it is not listed in the APP13007 Investigator's Brochure or is not listed at the specificity or severity that has been observed.

SUSARs with an outcome of death or are life threatening must be reported to the relevant Regulatory Authorities within 7 calendar days, all other SUSARs must be submitted within 15 calendar days. The SUSAR reporting procedures are detailed in the study Safety Management Plan. This plan is an agreement between the Sponsor, the CRO for Study Management and Monitoring and Drug Safety Navigator.

NOTE: The Sponsor will notify the appropriate regulatory agency and all participating site Investigators of any SUSARs (via the CRO for Study Management and Monitoring) on an expedited basis and in accordance with applicable regulations. In addition the sponsor is responsible for informing all Investigators in all ongoing studies involving the study drug about all SUSARs.

Medical and administrative data related to ICSRs which qualify for expedited and periodic reporting, should be provided in compliance with U.S. Food and Drug Administration (FDA) Code of Federal Regulations (CFR) 21, 312.32.

It is the responsibility of the Investigator to promptly notify the IRB and other appropriate institutional regulatory bodies of all unexpected serious adverse reactions involving risk to human subjects as per their applicable requirements.

9. SAFETY MANAGEMENT

9.1. Stopping Criteria

- Individual subject: Subjects with an IOP at POD1/pre-randomization > 30 mmHg will not be eligible for randomization and thus not enrolled in the study. After randomization to study drug, subjects with an IOP > 30 mmHg may continue the study drug and be treated with IOP lowering medication at the discretion of the Investigator. (Note: use of a prostaglandin-based treatment to lower IOP is prohibited).
- Individual subject: Subjects with an IOP > 30 mmHg after randomization who do not respond to IOP lowering therapy should discontinue study drug and should be treated at the Investigator's discretion. These subjects will continue in the study with scheduled assessments to be performed at each visit until EOS/POD28 (Part A) or EOS/POD22 (Part B).
- Individual subject: In consultation with the Study Medical Monitor, the Investigator should consider whether to stop study drug and rescue a subject with an IOP ≥ 24 mmHg AND an IOP increase ≥ 10 mmHg from pre-dose baseline (both criteria must be met).
- Study Treatments: Part A of the study will be conducted as planned. Key data (ACC, pain score, IOP, number of subjects rescued and AEs) from Part A will be evaluated by the Data Review Group in a masked manner and if necessary by the Sponsor Medical Monitor and Sponsor statistician in an unmasked manner after freezing the key data to determine whether Part B is to be conducted as planned. See Section 3.3 and Section 3.4 for further information on the decision-making process to determine whether Part B is conducted as planned or which alternative treatment option is to be used. The study sites, IRB and FDA will be informed of any changes to the planned treatment arms in Part B of the protocol before the changes are implemented.
- Study: The study can be stopped at any time if deemed necessary by the Sponsor's Medical Monitor in consultation with the Study Medical Monitor due to safety concerns. Additionally, safety will be monitored on an ongoing basis by the Data Review Group via periodic masked review of AEs and other safety endpoints. Specifically, if it is observed that visual acuity worsens by 2 lines at EOS in the treated study eye as compared to POD1, in 6 consecutive subjects, no further doses of study drug will be administered to any subjects in the study until

a comprehensive evaluation can be performed and, if possible, a cause is identified.

Safety assessments will be performed throughout the course of the study. The APP13007 Investigator's Brochure, Section 1.4.1 and the Risk Mitigation plan in Table 4 provide guidance for the Investigator on potential anticipated adverse events that may occur. Any potential safety issues that arise will be reviewed by the Study Medical Monitor in consultation with the Sponsor Medical Monitor to identify the appropriate course of action. If the Sponsor elects to terminate the study for any reason, the Investigator will be responsible for notification of the IRB and will withhold further dosing of study drug.

9.2. Dose Modification:

No dose modification is permitted.

All instances of missed doses must be recorded. If a subject is less than 75% compliant with dosing of study drug, the subject will be included in the 'Intention-to-Treat' analyses, but not in the 'Per Protocol' analyses for efficacy endpoints.

Note: Study drug bottle will be replaced if a bottle is lost or otherwise compromised before POD15 (see Section 5.1.2).

9.3. Dosing Interruptions

Investigator is not allowed to modify the dosing regimen due to AE or any other circumstance, but the Investigator has the option of stopping study drug after consultation with the Study Medical Monitor, if feasible. Subjects will be permitted to restart study drug if there is a temporary dosing interruption of study drug not more than 1 day due to an AE.

9.4. Rescue and Increased IOP Management

9.4.1. Criteria for Starting Rescue Medication

Any subject not responding adequately to the study drug at any time after randomization on POD1 may be rescued and placed on an appropriate alternative therapy determined by the Investigator. Subjects who, on examination of the anterior chamber, have one or more of the following criteria will be considered 'Rescued' subjects and should be discontinued from study drug dosing and placed on rescue mediation:

1. After randomization, anterior chamber cells count >30 cells.
2. After randomization, an increase in anterior chamber cell count by > 15 cells from POD1/pre-dose baseline.
3. After randomization, ≥ 2 grade of increase in anterior chamber flare from POD1/pre-dose baseline.

Initiation of rescue medication is at the discretion of the Investigator, following discussion with the Study Medical Monitor, even if none of the above criteria are met. However, it is recommended that the Investigator uses the above criteria to determine when to consider a subject for rescue medication.

Management

Investigators will use clinical judgment to determine the appropriate rescue medication to use and when to withdraw study drug and perform procedures.

While initiation of rescue medication is at the discretion of the Investigator, if one criterion above in Section 9.4.1 is met, the subject should be placed on rescue medication. Subjects not otherwise responding to study drug may be placed on alternative medication at the discretion of the Investigator even if none of the above criteria are met. In the situation where an investigator considers that alternative medication is required, but the above 'Rescue' criteria are not met, the subject is considered to be 'withdrawn' from the study and EOS assessments are to be performed. The choice of alternative medication is at the Investigator's discretion and will be used as directed by the Investigator. Any subject who is rescued based on the criteria in Section 6.3 and who is placed on rescue medication will discontinue the study drug and continue in the study for study assessments as described in Section 6.3.

A subject who is treated with an ocular corticosteroid or other anti-inflammatory product after POD22 (Part A) or POD15 (Part B) will be considered to be a 'Withdrawn' subject.

Rescued subjects will be considered treatment failures, but the need for rescue medication will not be considered as an AE. Rescued or Withdrawn subjects experiencing an AE at the time of rescue/withdrawal will be followed through by the Investigator to stabilization or resolution of the AE or the end of the study (whichever comes last). Rescued/Withdrawn subjects should be followed to resolution of signs and symptoms of an AE or until the Investigator has deemed the subject is stable.

Note:

Clarification of the distinction between 'Rescued' and 'Withdrawn':

i) Process for 'Rescued' subjects:

- *The subject notifies the clinical site and is able to return for an unscheduled visit or scheduled visit before starting rescue medication.*
- *The subject has a visit and the investigator documents that the subject meets one of the rescue criteria. The subject should be rescued. The study drug is stopped and the subject should be started on the investigator's preferred rescue medication.*
 - *EOT assessments are completed at the time of this evaluation and the subject returns for the EOS assessments as shown in Table 5A or Table 5B.*

- *The subject's status is 'Rescued' and the reason for rescue must be one of the rescue criteria. This information is entered into the source and eCRF.*

ii) *Process for 'Withdrawn' subjects:*

- *The subject notifies the clinical site and is able to return for an unscheduled visit or scheduled visit. At the visit, the investigator's opinion is that the subject needs to be withdrawn because of inadequate control of inflammation and pain, but one or more of the rescue criteria are not met. The subject is withdrawn from the study, and at the investigator's discretion, the study drug is discontinued and alternative medication is started to treat the subject.*
 - *At this site visit, the EOS evaluation is completed.*
- *The subject attends the clinical site for a scheduled visit and the investigator considers that the subject is inadequately treated by the study drug, but one or more of the rescue criteria are not met. The subject is withdrawn from the study because of inadequate control of inflammation and pain, and at the investigator's discretion, the study drug is discontinued and alternative medication is used to treat the subject.*
- *The subject contacts the clinical site without attendance, and the investigator considers that the subject is inadequately treated by the study drug for inflammation and pain. Then the subject should return at the next available opportunity for assessment to determine whether or not the rescue criteria are met. If not, the subject is withdrawn and the EOS assessments are completed.*
- *The subject's status is 'Withdrawn' from the study. The reason for subject withdrawal is recorded as "requiring alternate medication for inflammation and pain following cataract surgery" and any AEs should be recorded in the eCRF.*

If a subject is rescued, this event will be captured in the eCRF. Medications used for rescue will be recorded in the Concomitant Medications section of the eCRF. In addition, all the assessments in the check box with an (R) next to "X" in the Schedule of Events (Table 2A or Table 2B) shall be performed on subjects who are rescued.

9.4.2. Management of Increased IOP

Criteria for Starting IOP-Lowering Medication

Investigators should use the following criteria to determine whether to start IOP-lowering medication:

1. After randomization, an IOP > 30 mmHg
2. After randomization, an IOP ≥ 24 mmHg AND an increase of ≥ 10 mmHg from POD1/pre-dose baseline (both criteria must be met)

Initiation of IOP-lowering medication is at the discretion of the Investigator even if none of the above criteria are met, however, it is recommended that the Investigator uses these criteria to determine when to consider a subject for IOP-lowering medication.

Management

Investigator will use clinical judgment to determine the appropriate IOP-lowering medication to use and when to withdraw study drug and procedures, in consultation with the Study Medical Monitor.

After randomization and start of study drug, if a subject has an IOP > 30 mmHg the Investigator may commence non-prostaglandin-based IOP-lowering medication while continuing the study drug, with appropriate follow-up at the next planned visit or at an unscheduled visit. If IOP is < 30 mmHg at the next visit, the subject may continue on study drug. If at the next visit, the IOP remains > 30 mmHg while on IOP-lowering medication, then the study drug may be discontinued and alternative IOP-lowering medication may be started, after consultation with the Study Medical Monitor, who will then discuss with the Sponsor Medical Monitor.

After randomization and start of study drug, an IOP of ≥ 24 mmHg AND an increase ≥ 10 mmHg from the POD1/pre-dose baseline (both criteria must be met) is considered clinically significant and the Investigator should consider starting non-prostaglandin-based IOP-lowering medication while continuing the study drug, with appropriate follow-up at the next planned visit or at an unscheduled visit. If satisfactory reduction of IOP does not occur at the next visit, then the study drug may be discontinued after consultation with the Study Medical Monitor, who will then discuss with the Sponsor Medical Monitor.

Note:

Medications used for treating increased IOP will be recorded in the Concomitant Medications section of the eCRF.

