15. Have evidence of acute external ocular infections (bacterial, viral and/or fungal infections including vaccinia, varicella and other viral diseases of the cornea and conjunctiva); tuberculosis of the eye; intraocular infections, active chalazion, or uncontrolled blepharitis in the study eye
16. Have corneal dystrophies or dysthyroid ophthalmopathy in the study eye
17. Have uncontrolled and clinically significant dry eye syndrome in the study eye (mild dry eye with the use of artificial tears are allowed)
18. Have proliferative diabetic retinopathy (PDR), significant compromised macular function; significant macular diseases; clinically significant macular edema (CSME); or a history of cystoid macular edema in the study eye
19. Have had corneal or retinal surgery (laser or incisional) in the study eye within 6 months of the Screening visit, or be planning to have laser or incisional surgery during the study period in the study eye (other than cataract surgery)
20. Have surgery planned or scheduled for the contralateral eye during the study
21. Have previous ocular trauma with visible scarring or any deformities due to the trauma in the study eye that in the opinion of the Investigator may affect the pharmacokinetics of the study drug, or post-surgical outcome (including, but not limited to intraocular inflammation or the normal healing process)
22. Require the use of a contact lens or a collagen shield within 72 hours prior to cataract surgery or for the remainder of the study period in either eye
23. Require use of non-diagnostic topical ophthalmic medications in either eye for the duration of the study with the exception of the following which are allowed: mydriatics, anesthetics, antiseptics, balanced salt solution, viscoelastics, osmotic agents (e.g., Muro 128), prophylactic antibiotics, non-prostaglandin analog IOP lowering agents for IOP increases related to cataract surgery, lid scrubs for mild blepharitis, or artificial tears for the management of dry eye. Note: subjects requiring IOP lowering medications pre-surgery for ocular hypertension or glaucoma are excluded
24. Have the potential for ocular hemorrhage in the study eye that may interfere with evaluation of post-surgery inflammation

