5.6. Safety Analyses

Safety data will be analyzed for all subjects in the Safety population.

The safety endpoints are:

- Adverse event (AE)
- Serum cortisol concentrations (Part A)
- Clinical chemistry and hematology parameters (Part A) ([Appendix B](#))
- Intraocular pressure (IOP)
- Early Treatment Diabetic Retinopathy Study (ETDRS)

	Document Number: CLN.001.SAP	Version: 0
	Document Title: Clinical Study CPN-201 Statistical Analysis Plan	Page 23 of 35

- Best corrected Visual Acuity by pinhole method
- Slit-lamp biomicroscopy
 - Corneal edema
 - Ciliary flush
 - Bulbar conjunctival injection
- Dilated indirect ophthalmoscopy
 - Vitreous
 - Retina
 - Macula
 - Choroid
 - Optic nerve

See Section 7.2 of the protocol for detail about these endpoints. The analyses of these safety endpoints are described in the following sub-sections.

For all safety endpoints, the total number of subjects in the safety population and the summary statistics of all observed data will be calculated for each active dosing regimen and its matching vehicle placebo group and each visit as defined in the CRF. No imputation will be used.

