5.6.5. Intraocular Pressure

For both eyes at Screening and EOS, the analyses of IOP will follow the methods discussed in Section 5.3.2 for Both eyes at Screening and End of Study (EOS). The results will be presented in the top part of [Table 14.3.6.1](#) and [Table 14.3.6.2](#).

For study eye at POD1-POD22 (Part A) and POD1-POD15 (Part B), the analyses will follow the methods discussed in Section 5.3.2 for “observed data” under Study eye only. The results will be presented in [Table 14.3.6.1](#) and its CFB (Baseline = Screening for EOS; Baseline = POD1/pre-dose for other PODs) for the active and its matching vehicle placebo groups at each visit in [Table 14.3.6.2](#) and visually presented in [Figure 14.3.6.1](#).

The distribution of IOP over the ranges of <10, 10-15, 16-20, 21-25, 25-30, and >30(mmHg) for each treatment will be described by the frequencies in each range in [Table 14.3.6.3](#). The distribution of IOP increase over ranges of ≤ 0 , 1-5, 6-10, 11-15, >15 (mmHg) for the active and its matching vehicle placebo groups will be described by the frequency in each range at each visit in [Table 14.3.6.4](#).

	Document Number: CLN.001.SAP	Version: 0
	Document Title: Clinical Study CPN-201 Statistical Analysis Plan	Page 25 of 35

The number of subjects with an IOP ≥ 24 mmHg AND an increase ≥ 10 mmHg from pre-dose baseline, and the number of subjects with an IOP > 30 mmHg at any time following initiation of study drug will be summarized in the adverse event tables, [Table 14.3.1.1- 14.3.1.3](#).

All subjects' intraocular pressure information will be presented in [Listing 16.2.9.2](#) and visually presented in [Figure 14.3.6.2](#).

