6.5. Prior/concomitant/follow-up medications (including dictionary)

Prior/concomitant/follow-up medications, including rescue medications, will be coded using World Health Organization (WHO) Drug Dictionary WHODRUG B3 GLOBAL (MARCH 2019) and will be summarized by medication class and medication name presented for each active dosing regimen and its matching vehicle placebo group for the safety population in [Table 14.1.5](#).

All prior/concomitant/follow-up medications will be presented in [Listing 16.2.9.1](#).

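### IOP is compared between arms as observed, with no account of IOP-lowering medication, so a steroid effect can be understated at later visits and in the threshold counts

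*Protocol*

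**What the plan says.** **Use of IOP-lowering medication**
- Protocol 9.4.2 gives two criteria after randomization: IOP above 30 mmHg, or IOP of at least 24 mmHg with a rise of at least 10 mmHg from POD1. It then states: "Initiation of IOP-lowering medication is at the discretion of the Investigator even if none of the above criteria are met". The same sentence recommends using the criteria.
- For a subject above 30 mmHg, the investigator "may commence non-prostaglandin-based IOP-lowering medication while continuing the study drug". Similar wording covers the second criterion. For starts below both criteria, 9.4.2 does not say whether study drug continues, and it does not require stopping.
- Exclusion criterion 23 (Protocol 4.3) lists among the permitted eye medications "non-prostaglandin analog IOP lowering agents for IOP increases related to cataract surgery". It gives no start or stop day.
- Recording is covered: "Medications used for treating increased IOP will be recorded in the Concomitant Medications section of the eCRF". Protocol 5.4 adds start and stop dates, eye treated and reason for use.

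**Analysis of IOP**
- SAP 5.6 applies to all safety endpoints: "No imputation will be used".
- SAP 5.6.5: "For study eye at POD1-POD22 (Part A) and POD1-POD15 (Part B), the analyses will follow the methods discussed in Section 5.3.2", meaning the observed-data method for the study eye. It plans IOP and change from baseline by visit, frequencies over IOP bands and over increase bands at each visit, figures and a listing.
- SAP 5.6.5 also plans two counts: "The number of subjects with an IOP ≥ 24 mmHg AND an increase ≥ 10 mmHg from pre-dose baseline", and the number above 30 mmHg at any time after study drug starts.
- The SAP Appendix adds between-arm comparisons of IOP means and changes from baseline.
- SAP 6.5 covers prior, concomitant and follow-up medications together; these "will be summarized by medication class and medication name presented for each active dosing regimen" and its matching vehicle.

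No IOP analysis marks a value measured under IOP-lowering medication or treats the start of that medication as an outcome.

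**The concern.** Raised IOP is the first class-related ocular risk named in Protocol 1.4.1. This is the first human use of the product (Protocol 1.4.2), and the study is meant to choose a regimen for Phase 3 (SAP 1). IOP-lowering medication acts directly on the variable being compared, and a rising pressure is what prompts it. If a potent steroid leads to more treatment than vehicle does, the treated readings pull the active arm back toward vehicle. For efficacy, SAP 5.1.6.2 handles rescue explicitly as an event after baseline. IOP has no equivalent rule.

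At stake is how a null IOP comparison is read. It could mean that the drug did not raise IOP, or that it did and the rises were treated. The planned IOP tables cannot separate the two.

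**Working it through.** **1. The plan's own figure.** No document sizes the trial for IOP. The only sizing figure is 21 per arm, to leave about 20 completers at 5% dropout: 20 / 0.95 = 21.05, and 21 × 0.95 = 19.95. It reproduces, so n = 21 is used below.

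**2. What the threshold counts can miss.** In whole mmHg, with POD1 value b, the lowest counted reading is min(max(24, b + 10), 31). The largest uncounted rise is that reading minus 1 minus b.

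| POD1 IOP | Lowest counted reading | Largest uncounted rise |
|---|---|---|
| 12 | 24 | 11 |
| 16 | 26 | 9 |
| 20 | 30 | 9 |
| 24 | 31 | 6 |
| 28 | 31 | 2 |

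A rise treated within this range, and kept there, enters neither count.

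**3. One invented subject followed through the tables.** POD1 is 14 and POD8 is 23 (+9). Drops are started, and POD15 is 17 (+3).
- POD8: the value enters the mean and change, the 21-25 band and the 6-10 increase band.
- POD15: it enters the mean and change, the 16-20 band and the 1-5 increase band, with no sign of treatment.
- Neither threshold count includes the subject.

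The rise is therefore visible once, at the visit where it was measured. After that it is attenuated.

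**4. Effect on later-visit means.** If k active subjects are treated with an average lowering of r mmHg, and no vehicle subject is treated, the active mean falls by k × r / 21. If vehicle subjects are treated too, k becomes the difference in numbers treated, for equal r. Both k and r are assumptions.
- k = 1, r = 3: 3 / 21 = 0.14 mmHg
- k = 2, r = 5: 10 / 21 = 0.48 mmHg
- k = 4, r = 7: 28 / 21 = 1.33 mmHg

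For scale, the standard error of an arm difference is SD × √(2/21): 0.93, 1.23 and 1.54 mmHg at assumed SDs of 3, 4 and 5. At SD 4 the range is 0.12 to 1.08 standard errors.

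**5. Effect on threshold counts.** Assume that 4 active and 0 vehicle subjects would cross a threshold if untreated.
- None kept below by early treatment: 4/21 − 0 = 19.0 percentage points
- Two kept below: 2/21 = 9.5 points
- All four kept below: 0.0 points

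A composite of threshold crossing or start of IOP-lowering medication counts all 4 (19.0 points) in each case.

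**6. What the other tables add.** SAP 6.5 gives class and name by arm, but pools prior, concomitant and follow-up use and shows neither the day nor the IOP at start. The SAP Appendix defines surgical medications as routine cataract-surgery drugs used up to 1 day after surgery, so drops begun on POD1 could fall there. The IOP-specific adverse event rules in Protocol 8.1 use the same two thresholds.

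**The case against.** The strongest reply is that the SAP already shows most of what matters. It plans more than threshold crossings: means, changes, two sets of bands, figures and a listing, with the Appendix comparisons on top. The reading that prompts treatment is normally already in the data, and a crossing before treatment stays counted. Drug use is tabulated by arm. Protocol 7.3.1 makes clinically relevant deterioration an adverse event. As-observed safety analysis is a deliberate choice, there are no formal hypotheses, and p-values are descriptive.

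Much of this stands, and it rules out several stronger readings that a reader might infer:
- **That treated rises disappear, or that only crossings are analysed.** SAP 5.6.5 contradicts this. The effect is attenuation at later visits and omission from two counts.
- **That a high POD1 value hides a later rise.** A subject at 29 on POD1 would need 39 to meet the +10 condition, but the separate count catches that subject at 31. A pre-dose surgical rise also precedes randomization, and the absolute IOP bands do not use POD1.
- **That drops are expressly allowed from POD1, or that study drug expressly continues after every start.** Exclusion 23 gives no day, and 9.4.2 writes the continuation only for subjects who meet a criterion.
- **That each early start removes an event.** This presumes the subject would otherwise have crossed.

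The reply does not supply a by-arm count of starts after first dose, or any mark on treated values. Adverse event reporting is not a sure backstop either: Protocol 8.1 keeps events judged normal for cataract surgery in the source documents.

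**Conclusion.** The point holds in a limited form. IOP-lowering medication may be started below both criteria, and the IOP analyses ignore it. Later-visit IOP can be attenuated, and rises treated below threshold are missed by both threshold counts. The direction is toward no difference only if more active than vehicle subjects are treated. That is plausible for a potent steroid, but the documents do not establish it.

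The size is unknown, because the documents give no treatment rate, pressure-lowering effect or SD. Under the stated assumptions the active mean shifts by 0.14 to 1.33 mmHg, and each averted crossing removes 1/21 = 4.8 points from that arm's count. No error rate is affected. This is an inexpensive improvement on an important safety question, not a flaw that invalidates the IOP analysis.

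**What to change.** In SAP 5.6.5 add, by arm:
1. The number of subjects starting or escalating IOP-lowering medication in the study eye after first dose, with POD and IOP at start. Flag separately those already on such drops at POD1.
2. Alongside the two existing counts, a supplementary composite: IOP above 30, or at least 24 with a rise of at least 10, or IOP-lowering medication started after first dose.
3. A flag on IOP values measured under such medication, and a by-visit summary that excludes them. Exclusion drops the subjects who needed treatment, so read it beside the composite and not as a bias correction.

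Do not carry a pre-treatment value forward. That would hold a possibly transient peak through later visits and conflict with the no-imputation rule.

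**Cost.** SAP wording and one flag derived from medication dates, eye and reason already recorded. Some discretionary or surgery-related starts will count in the composite, so it should stay supplementary. If the SAP is closed, SAP 1 permits further hypothesis-generating analyses, labelled as additions.

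**To reconcile at the same time**
- SAP 5.6 uses all observed data, while the 5.3.2 method cited in 5.6.5 keeps only data while on study drug. Under the latter, subjects who stop study drug for unresponsive IOP but continue visits (Protocol 9.1) leave the by-visit IOP tables.
- Protocol 5.4.2 and 5.4.3 ban eye drops after randomization, with listed exceptions that do not include IOP-lowering agents. Exclusion 23, 9.1 and 9.4.2 allow such agents.

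The clinical management rules need no change for this analysis.
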